6.3 Exclusion criteria

For an eligible subject, all exclusion criteria must be answered “no”.

1. Previous participation in this trial. Participation is defined as signed informed consent
2. Known or suspected hypersensitivity to trial product or related products
3. Receipt of any investigational medicinal product (IMP) within 30 days prior to the day of screening (Visit 1)
4. Previous insulin intensification regimen for more than 14 days: premixed insulin thrice daily, basal-bolus regimen or continuous subcutaneous insulin infusion (CSII). Treatment during hospitalisation or during gestational diabetes is allowed for periods longer than 14 days
5. Treatment with any medication for the indication of diabetes or obesity other than stated in the inclusion criteria in a period of 90 days before the day of screening (Visit 1)
6. Anticipated initiation or change in concomitant medications for more than 14 consecutive days or on a frequent basis known to affect weight or glucose metabolism (e.g. orlistat, thyroid hormones, systemic corticosteroids)
7. Use of non-herbal Chinese medicine or other non-herbal local medicine with unknown/unspecified content within 90 days prior to the day of screening (Visit 1). Herbal traditional Chinese medicine or other local herbal medicines may, at the investigator's discretion, be continued throughout the trial
8. Subjects presently classified as being in New York Heart Association (NYHA)¹¹ Class IV
9. Planned coronary, carotid or peripheral artery revascularisation on the day of screening
10. Impaired liver function, defined as ALT \geq 2.5 times upper normal limit at screening
11. Proliferative retinopathy or maculopathy requiring acute treatment. Verified by fundus photography or dilated fundoscopy performed within 90 days prior to randomisation (Visit 2)
12. Female who is pregnant, breast-feeding or intends to become pregnant or is of childbearing potential not using an adequate contraceptive method (adequate contraceptive measure as required by local regulation or practice)

China: sterilisation, intrauterine device (IUD), oral contraceptives or barrier methods.

13. History or presence of malignant neoplasms within the last 5 years (except basal and squamous cell skin cancer and in-situ carcinomas)
14. Any contraindications to BIAsp 30 or metformin according to local label
15. Mental incapacity, unwillingness or language barrier precluding adequate understanding or cooperation, as judged by the investigator
16. Any disorder which, in the opinion of the investigator might jeopardise subject's safety or compliance with the protocol

6.4 Withdrawal criteria

The subject may withdraw at will at any time. The subject's request to discontinue must always be respected.

The subject may be withdrawn from the trial at the discretion of the investigator due to a safety concern or if judged non-compliant with trial procedures.

The subject must be withdrawn from the trial if the following applies:

1. Included in the trial in violation of the inclusion and/or exclusion criteria
2. Pregnancy
3. Intention of becoming pregnant
4. Participation in another clinical trial throughout the trial

6.5 Subject replacement

Subjects who are withdrawn will not be replaced.

6.6 Rationale for trial population

The trial population consists of subjects with type 2 diabetes on basal insulin and OAD treatment who have failed to achieve appropriate glycaemic control. These subjects, often presenting with HbA_{1c} between 7.5 and 10.0% (both inclusive), are expected to benefit from insulin intensification and optimisation. One of the choices for insulin intensification will be premixed insulin such as BIAsp 30.

It is expected that some subjects in the target population will be on one other OAD in addition to metformin. At randomisation, subjects will be stratified according to whether or not they have received treatment with metformin, with or without one other OAD.

Both insulin NPH OD/BID and basal insulin analogue OD are commonly used basal insulin regimen in many countries. In order to mimic the practice in clinical setting, the majority (approximately 80%) of subjects included into this trial will be those on basal insulin analogue prior to the trial.

Based on that, subjects with type 2 diabetes who are inadequately controlled on basal insulin combined with metformin with or without one additional OAD will be included in the trial, as they are expected to benefit from premixed insulin either TID or BID regimen.

7 Milestones

Planned duration of recruitment period (i.e. FPFV–LPFV): 48 weeks

End of trial (P27) is defined as LPLV.

Recruitment:

The screening and randomisation rate will be followed closely via the interactive voice/web response system (IV/WRS) in order to estimate when to stop screening. Within each participating country it will be aimed at including a maximum of 20% of randomised subjects on treatment with NPH prior to screening. All investigators will be notified immediately when the recruitment period ends, after which no further subjects may be screened and the IV/WRS will be closed for further screening. All subjects included in the screening period and eligible for randomisation can be randomised.

Trial registration:

Information of the trial will be disclosed at clinicaltrials.gov and novonordisk-trials.com. According to the Novo Nordisk Code of Conduct for Clinical Trial Disclosure¹², it will also be disclosed according to other applicable requirements such as those of the International Committee of Medical Journal Editors (ICMJE)¹³, the Food and Drug Administration Amendment Act (FDAAA)¹⁴, European Commission Requirements^{15,16} and other relevant recommendations or regulations. If a subject requests to be included in the trial via the Novo Nordisk e-mail contact at these web sites, Novo Nordisk may disclose the investigator's contact details to the subject. As a result of increasing requirements for transparency, some countries require public disclosure of investigator names and their affiliations.

8 Methods and assessments

8.1 Visit procedures

Throughout the trial the investigator must ensure working in accordance with International Conference on Harmonisation Good Clinical Practice (ICH GCP)¹ and local regulations. The investigator must ensure that trial procedures are performed as described in the protocol. Any discrepancies will result in protocol and/or GCP deviations and the investigator must take appropriate action to avoid recurrence of the detected discrepancies.

The investigator must keep a log of staff and delegation of task(s) at the site. The investigator must sign the log of staff and delegation of task(s) at site at the time of delegation.

The subjects will be asked to attend a screening visit, a randomisation visit, 6 clinic visits and 17 phone contacts during the treatment period, an end-of-treatment visit and a follow-up phone contact

Review of laboratory reports, patient reported outcomes (PROs), diaries etc. must be documented either on the documents and/or in the subject's medical record.

If clarification of entries or discrepancies in the diary or PROs is needed, the subject must be questioned and a conclusion made in the subject's medical record. Care must be taken not to bias the subject.

The following sections describe the assessments and procedures. These are also included in the flow chart (Section [2](#)).

8.1.1 Informed consent

Before screening takes place, potential subjects must be provided with written and oral information about the trial and the procedures involved, in accordance with local requirements. Subjects will be fully informed, orally and in writing, of their responsibilities and rights while participating in the trial, as well as of possible advantages/disadvantages when being treated with the trial medication. Subjects will have the opportunity to ask questions, and have ample time to consider participation.

Subjects who wish to participate in the trial must sign and date the subject information/informed consent form (SI/IC) before any trial-related procedures (Section [18.3](#)). All subjects must be provided with a copy of their signed and dated informed consent form(s).

The informed consent process may take place before the screening visit (Visit 1).

8.1.2 Screening visit (Visit 1)

The investigator must keep a subject screening log, a subject identification code list and a subject enrolment log. The subject screening log and subject enrolment log may be combined in one list and may be generated from IV/WRS.

At screening, subjects will be provided with a card stating that they are participating in a trial and giving contact address(es) and telephone number(s) of relevant trial site staff. Subjects should be instructed to return the card to the investigator at the last trial visit or to destroy the card after the last visit.

Each subject will be assigned a unique 6-digit subject number which will remain the same throughout the trial. The screening session must be made in the IV/WRS.

The investigator must document the review and evaluation of all screening data, especially how subjects fulfil the eligibility criteria. The assessments and blood samplings listed in the flow chart (see Section [2](#)) for the screening visit should be performed according to Section [8](#) and relevant data recorded in the electronic case report form (eCRF).

8.1.3 Screening failures

If any inclusion criterion is answered “no” or any exclusion criterion is answered “yes”, the subject is a screening failure.

For screening failures the screening failure form in the eCRF must be completed with the reason for not continuing in the trial. Serious and non-serious adverse events (AEs) from screening failures must be transcribed by the investigator into the eCRF. Follow-up of serious adverse events (SAEs) must be carried out according to Section [12](#).

A screening failure session must be made in the IV/WRS. The case book must be signed.

8.1.4 Re-screening

Re-sampling or re-screening is NOT allowed if the subject has failed one of the inclusion or exclusion criteria related to laboratory parameters. Re-screening is NOT allowed in any case.

8.1.5 Randomisation visit (Visit 2) and treatment period

Eligible subjects will attend the randomisation visit no later than 14 days following the screening visit. The procedures and assessments listed in the flow chart (Section [2](#)) for the randomisation visit must be performed. All inclusion and exclusion criteria must be checked again to confirm the subject’s eligibility and relevant data will be recorded in the eCRF.

A randomisation session in the IV/WRS will be performed whereby eligible subjects will be randomised either to the BIAsp 30 TID or BIAsp 30 BID arm, both in combination with metformin.

Relevant training of the subject in the use of the trial product will be conducted by the investigator or designated staff.

Following randomisation, subjects will undergo 24 weeks of treatment. The treatment period consists of 6 clinic visits and 17 phone contacts. The investigator should use the IV/WRS drug accountability module and confirm dispensing of allocated trial products at each dispensing visit (Section 9.4). The IV/WRS will allocate trial product to the subjects. All procedures and assessments listed in the flow chart in Section 2 for treatment period should be performed and relevant data will be recorded in the eCRF. Insulin dose will be titrated in accordance with the titration guideline in Appendix A.

Subjects must attend the randomisation visit (Visit 2) and Visit 14 in a fasting state. Fasting is defined as no food or drink intake, except water, after midnight prior to the visit. Trial product, metformin and any medication which should be taken with or after a meal must be withheld on the day of the visit until blood sampling and body weight measurements have been performed. Any other concomitant medication should be taken as usual.

If the subject is not fasting as required, all other assessments can be performed except for blood sampling and body weight measurement which must be rescheduled within the visit window. The date of the fasting assessment must be documented in the medical record and entered accordingly in the eCRF. Rescheduling of fasting visits/assessments is not considered an unscheduled visit.

The investigator must document review and evaluation of all data which has been reported during the phone contacts. If discrepancies are found i.e. in the diary once the subject attends a clinic visit, the subject must be questioned and a conclusion made in the subject's medical record.

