8.1.6 End-of-treatment visit (Visit 26)

All procedures and assessments listed in the flow chart in Section 2 for end-of-treatment should be performed and relevant data will be recorded in the eCRF.

Subjects must attend the end-of-treatment visit fasting according to the definition in Section 8.1.5.

The end-of-treatment form must be completed, final drug accountability performed and a completion session made in the IV/WRS. The case book must be signed.

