8.5.2.2 Lipids

Blood samples for lipids will be taken at Visit 2 and Visit 26, and the analysis consists of:

- Cholesterol
- High density lipoprotein (HDL) cholesterol
- Low density lipoprotein (LDL) cholesterol
- Triglycerides

Any abnormal, clinically significant findings that occur as part of the baseline assessments prior to any trial product provided (Visit 2) must be reported as concomitant illness. Any clinically significant worsening from Visit 2 onwards must be recorded as an AE (Section [12](#)).

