8.8 Unscheduled visits

In case further titration is needed or an adverse event (AE) occurs that requires further attention, extra visits can be arranged. If laboratory samples need to be re-taken due to missing result(s) (e.g. haemolysed, sample leaked during transit, sample not being conclusive, lost in transit etc.), the subject should be called in for an unscheduled visit. The repeated blood sampling must be marked with the related visit number. The last sample will be conclusive. It should be specified which visit number the unscheduled visits is related to in the eCRF.

An unscheduled visit form must be completed in the eCRF indicating the reason for the visit e.g.:

- Adverse event (AE)
- Laboratory re-sampling
- Other

If the subject attends the clinic to obtain additional product or auxiliary supplies then this should **NOT** be recorded as an unscheduled visit. In this case an additional dispensing session should be made in the IV/WRS and the Subject's medical record should be updated accordingly.

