8.9 Re-scheduled visits

If the Subject attends the fasting visits in a non-fasting condition all blood samples, body weight must be re-scheduled within the visit window. The date of the laboratory sampling and body weight measurement in the eCRF should reflect the actual date of the re-sampling/body weight measurement, i.e. the actual visit date will differ from the assessment date under the same visit.

9 Trial supplies

Trial supplies comprise trial products and auxiliary supplies. Additional details regarding trial supplies can be found in the Trial Materials Manual (TMM).

Trial products must not be dispensed to any person not included in the trial.

BIAsp 30 must not be used, if it does not appear white and cloudy after resuspension.

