Presentation of results from a statistical analysis of a continuous endpoint analysed by a mixed model for repeated measurements (MMRM) analysis will include the estimated mean (= Least Square Mean) change from baseline for each treatment as well as the estimated mean treatment difference including a two-sided 95% confidence interval and a p-value for test of no difference between treatments.

If an assessment has been made both at screening and randomisation, and if not otherwise specified, the value from the randomisation visit will be used as the baseline value. If the value measured at the randomisation visit is missing and the assessment also has been made at screening, then the screening value will be used as the baseline value. If an assessment is only made at randomisation or at screening the relevant value will be the baseline value.

For efficacy variables missing values will not be replaced by imputed values unless otherwise specified. In the primary analysis missing values are handled by a MMRM.

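### A Visit 2 blood sample re-drawn after the first dose can count as baseline, because re-draws and baseline go by visit label and not by dosing date

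*Combined protocol and SAP*

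**What the plan says.** **Re-draws.** Section 8.8 recalls a subject whose laboratory result is missing, for example because the sample was haemolysed or lost. It then states: "The repeated blood sampling must be marked with the related visit number. The last sample will be conclusive". It gives no time limit and no condition relative to dosing.

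**Baseline.** Under the introduction to Section 17, where an assessment is made at both screening and randomisation, "the value from the randomisation visit will be used as the baseline value". Screening is used only if the randomisation value is missing. An assessment made at only one of the two visits takes its baseline from that visit. Neither rule mentions the first dose.

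**Fasting visits.** Section 8.1.5 says trial product "must be withheld on the day of the visit until blood sampling and body weight measurements have been performed". For a subject who arrives non-fasting, "all other assessments can be performed except for blood sampling and body weight measurement which must be rescheduled within the visit window". Section 8.9 adds that "the actual visit date will differ from the assessment date under the same visit".

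**Intended order.** Section 8.5.2.2 (lipids) describes the Visit 2 baseline assessments as coming before any trial product is provided.

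**Visit 26.** Section 8.1.6: "Subjects must attend the end-of-treatment visit fasting according to the definition in Section 8.1.5". The same section has "final drug accountability performed and a completion session made in the IV/WRS". Section 5.4 has subjects move to a marketed product when trial product stops.

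**The concern.** Baseline should precede treatment. The documents intend this, since Sections 8.1.5 and 8.5.2.2 both put sampling before trial product. The re-draw rule and the baseline definition do not carry that order over. A late replacement sample takes the Visit 2 label, so it becomes the baseline even if the subject has already stopped basal insulin and other OADs and started BIAsp 30.

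For FPG, which Section 17.4.1.1 models like the primary endpoint, such a value would enter twice: in the change score and as the covariate. For lipids it would distort descriptive summaries and shift tables. At Visit 26 the mirror case is a week-24 value taken after trial insulin has ended.

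**Working it through.** **1. Re-draw route at Visit 2.**
- Section 8.5 sends all analyses except the urine pregnancy test to a central laboratory, so a lost or haemolysed Visit 2 sample would normally come to light after the visit.
- Sections 8.1.5 and 11 place randomisation at Visit 2. Section 5.3 stops pre-trial basal insulin and other OADs at randomisation, and Section 9.4 allocates trial product at Visit 2.
- Section 8.8 labels the re-draw Visit 2 and lets it decide. Section 17 then takes it as baseline.
- FPG is scheduled at Visits 2, 14 and 26 (Section 8.5.1.2) and lipids at Visits 2 and 26 (Section 8.5.2.2). Neither has a screening value to fall back on.
- Where a screening value does exist, the fallback is not triggered, because the Visit 2 value is not missing.
- Body weight is not exposed here, because Section 8.8 concerns laboratory samples only.

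**2. Fasting route at Visit 2.** Blood and weight move to another date within the visit window. The withholding rule covers only the day of the visit. Whether the new date can fall after the first dose depends on the Visit 2 window, and that row of the flow chart is not legible in the text reviewed. This route is possible but not established.

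**3. Visit 26.** Sections 8.1.6, 8.8 and 8.9 do not tie a rescheduled or re-drawn sample to time on trial product. Sections 17, 17.3 and 17.4.1.1 do not restrict week-24 values to that time.

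**4. Sample size, reproduced.** Inputs from Section 17.1: difference 0.3%, SD 1.1%, two-sided 5%, 213 per arm. The noncentrality is 0.3 / (1.1 × √(2/213)) = 2.81 on 424 degrees of freedom, giving power of 80.2%. The stated 426 reproduces exactly, and this point does not change it.

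**5. Size for FPG (assumed inputs).** Let f be the share of subjects affected and s the FPG movement by the time of the late sample.
- Subjects: 0.02 × 426 ≈ 9; 0.05 × 426 ≈ 21.
- Shift in an arm's mean change = f × s: 0.02 × 1 = 0.02 mmol/L; 0.05 × 2 = 0.10 mmol/L.
- The trial estimates TID minus BID. If f is equal in the arms and the early between-arm gap is g, the baseline imbalance is f × g. With g = 0.5 mmol/L, also assumed, it is 0.05 × 0.5 = 0.025 mmol/L.
- With baseline as covariate, the adjusted difference moves by b × 0.025, where b is the slope of the post-treatment value on baseline. For b between 0 and 1 this is at most 0.025 mmol/L.

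**6. Size for week-24 HbA1c (assumed inputs).** Suppose a share f of values has lost a fraction r of the 0.3% difference. The detectable difference becomes 0.3 × (1 − f × r).

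| f | r | Difference (%) | Power |
|---|---|---|---|
| 2% | 10% | 0.2994 | 80.0% |
| 5% | 10% | 0.2985 | 79.8% |
| 5% | 50% | 0.2925 | 78.2% |

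The last row is a stress case. A delay of a few days should sit nearer the first two.

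**The case against.** **A stronger reading is tempting on the fasting route.** A reader might infer that a non-fasting subject is randomised, given trial product and dosed at Visit 2, with baseline blood and weight taken days later on treatment. The documents do not support that as stated. Section 8.1.5 lets the other assessments proceed; it does not say that randomisation or first dosing does. Rescheduling is bounded by the visit window. If that window has no days after randomisation, the route closes for Visit 2, and with it all exposure of baseline weight. Nor does the legible text show an HbA1c sample at Visit 2.

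**The problem can be traced.** Sections 8.1.5 and 8.9 require the actual assessment date for rescheduled measurements, and Section 8.6.2 records the first and last days of BIAsp 30. Late samples can be found, and Section 17 leaves room for an SAP before database lock. This stands, and it makes the repair cheap, but as written the rules still use the late value.

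**The effect largely cancels.** Sample loss should not depend on arm, and a subject arrives non-fasting before allocation is known. Both arms start at the same unit-for-unit total dose (Section 5.3.1), with the first titration contact at week 1. This stands for prompt re-draws. It weakens if a re-draw comes weeks later, which Section 8.8 does not rule out.

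**Flow-chart note 3 might seem to block the re-draw route**, since it requires all results before randomisation. With randomisation at Visit 2 and samples sent to a central laboratory, results from that visit's own samples cannot ordinarily be awaited.

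**Discarding every late Visit 26 sample would do harm.** It would turn usable week-24 HbA1c values into missing data resting on the missing-at-random assumption of Section 17.3, although HbA1c moves little in a few days. This objection is accepted.

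**Conclusion.** The point holds for laboratory re-draws. Sections 8.8 and 17 together allow an on-treatment sample to serve as baseline, contrary to the order set in Sections 8.1.5 and 8.5.2.2. The endpoint mainly affected is FPG, a supportive modelled endpoint; lipids are descriptive only. For Visit 2 blood and weight under the fasting rule, the point depends on the visit window. At Visit 26 the plan is silent on whether late values reflect trial insulin.

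The size is small: 0.02–0.10 mmol/L in one arm's mean FPG change, and about 0.025 mmol/L or less between arms in the worked illustration. These figures rest on an assumed 2–5% of subjects affected, an assumed 1–2 mmol/L movement and an assumed 0.5 mmol/L early gap, none of which is in the documents. A reader might infer that the primary comparison is biased; nothing here supports that. The case for correction is that a stated rule can yield a wrong baseline and is cheap to repair.

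**What to change.** - **Section 17 (or an SAP before database lock):** define baseline as the last value obtained before the first dose of trial product. A Visit 2-labelled value taken later is not a baseline. Use the screening value where one exists; otherwise baseline is missing.
- **Sections 8.1.5, 8.8 and 8.9:** state that Visit 2 fasting blood and weight are taken before the first dose. A non-fasting subject has Visit 2 re-booked within the existing 14 days from screening.
- **Visit 26:** keep a late HbA1c re-draw in the primary analysis. Flag FPG and weight values taken after the last trial dose, and add a sensitivity analysis excluding them.
- **Dates:** use those already required. For Section 8.8 re-draws, confirm that the sampling date is held alongside the related visit number.

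**Cost:** wording changes, a few re-booked Visit 2 appointments, and a few missing baseline FPG or lipid values. A subject without baseline FPG has no change score and drops out of that model. A weight that falls back to Visit 1 may not be fasting, since Section 8.4.8.2 marks only Visits 2, 14 and 26 as fasting.
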